3.1 Population

Three hundred participants will be included. Men and women aged 18 to 80 yrs, at risk for metabolic syndrome, will be eligible.

3.2 *Sample size calculation*

In each pilot intervention, 100 participants will be divided in 5 subgroups of 20 participants, each receiving a BEF within a specific food matrix (dairy-, bakery-, egg products) enriched with DHA, BG or AC alone, or DHA+BG, or DHA+AC. In this exploratory study, within each matrix, 20 subjects per arm would be sufficient to obtain measurable changes for the parameters that will be tested.

3.3 *Inclusion criteria*

MS is defined when three of the following criteria are met:

- elevated waist circumference (men \geq 102 cm; women \geq 88 cm)
- elevated fasting triglycerides (\geq 150 mg/dL)
- reduced fasting HDL-cholesterol (men \leq 40 mg/dL; women \leq 50 mg/dL)
- elevated blood pressure (systolic \geq 130 mmHg and/or diastolic \geq 85 mmHg) or hypotensive treatment
- elevated fasting glucose (\geq 110 mg/dL)

Subjects will be eligible to the pilot study if they present with two to four of the MS criteria, at least one of them being alteration of fasting triglycerides or HDL-C cholesterol.

3.4 *Exclusion criteria*

Participants are excluded if three or more clinical criteria for metabolic syndrome are met. Additionally, major exclusion criteria are:

- regular drug therapy with impact on serum lipids;
- diabetes (fasting glucose $>$ 1.26 g/L, or anti-diabetic treatment);
- recent history of cancer or cancer treatment (less than 2 years);
- active or recently diagnosed intestinal malabsorption or disorders associated with malabsorption: Crohn's disease, short bowel syndrome, Pancreatic insufficiency, cystic fibrosis, Tropical Sprue, whipple's disease, chronic pancreatitis, gastrojejunostomy, surgical treatments for obesity, cholestasis, biliary atresia, parasite infections, HIV/AIDS
- familial dyslipidemia;
- use of medication known to cause malabsorption: tetracycline, cholestyramine, thiazide diuretics, aluminium/magnesium hydroxide, cochlincine, neomycin, methotrexate, methyl dopa, and allopurinol, and laxatives
- illegal drug use, chronic alcoholism or active smoking;
- consumption of nutritional supplements containing DHA, BG or AC;
- history of allergy or intolerance to any components used in BEFs, celiac disease, lactose intolerance, allergy to milk or egg proteins;
- institutionalised patients, those who lack autonomy to consent or are unable to meet all examinations;

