6.1 Randomization

The study will be double-blinded (blinded for the study subjects as well as for the investigator). Throughout the trial the blind must not be broken, only in case of emergency, in which case sealed emergency envelopes containing the name of the enrichment material will be available. The consumption of experimental product must be discontinued if the code has been broken for any reason. Every code breaking has to be reported to the WP5 leader.

A total number of 300 participants will be enrolled into the study. The complete sample size will be equally distributed between three centres responsible for either bakery, dairy or egg products, which results in a sample size of 100 per centre. In each centre participants will be divided in 5 groups of 20 each receiving BEF formulated using a specific matrix (bakery, dairy or egg-based), and enriched with DHA, BG, or AC alone or DHA+BG, or DHA+AC. The allocation of participants to the different groups will be carried out based on predefined randomization lists created separately for each pilot study. All three randomization lists will be prepared with a sample size of 120, with a block size of 5 and with an allocation ratio of 1:1:1:1:1. In case of withdrawn of a volunteer, he/she will be substituted by a new one. For this purpose, an additional sample size of 20 will be applied for each pilot study. Gender will be considered as a stratum with a ratio near to 1:1. Each randomization list will consist of a three-digit randomization number from 101 to 160 for male and from 201 to 260 for female participants with the name and code of the assigned enrichment material. The prepared randomization lists will be sent to the manufacturers of each product, who will pack and label the products according the list and send them to the centres.

A three-digit unique randomization number will be assigned to each individual recruited volunteer, which will determine the allocation of the products. Randomization numbers will be distributed in ascending order with the starting number of 101 in each centre. Centres will also get a unique one-digit centre identifier. Therefore volunteers will be identified by a centre and a participant codes.

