6.3.1 Analysis Datasets

- The full analysis dataset (FAS) is defined as all randomized subjects who received at least one dose of experimental product and have primary outcome data both at baseline and at the end of the study.

- The safety analysis dataset (SD) is defined as all randomized subjects who received at least one dose of experimental product.

A total number of 300 participants will be enrolled into the study. The complete sample size will be equally distributed between three centres responsible for either bakery, dairy or egg products, which results in a sample size of 100 per centre. In each centre participants will be divided in 5 groups of 20 each receiving BEF from a specific matrix, and enriched with DHA, BG, or AC alone or DHA+BG, or DHA+AC. The allocation of patients to the different groups will be carried out based on predefined randomization lists created separately for each pilot study.

6.4 *Statistical Analysis*

The primary and secondary analyses will be performed on the FAS dataset. Descriptive statistics for both of the primary and secondary variables will also be provided on the SD dataset. The evaluation will be done using the SAS 9.2 (or later) program package version.

Mean change in blood TG and HDL-cholesterol (primary endpoints) will be analyzed with a mixed linear model including food matrix and type of enrichment as fixed effects. If the model indicates significant differences among groups, post-hoc tests will be applied for pair wise comparisons.

Secondary endpoint variables will be analyzed similarly. Descriptive statistics for both of the primary and secondary parameters will be provided including the mean, median, minimum, maximum, standard deviation, standard error of the mean and number of cases. Mean changes (and their 95% CI) from baseline to end-of-study visit will be presented.

For safety data, descriptive statistics and individual listings of eventual adverse events (adverse events linked to venous punctures, digestive troubles following BEF ingestion, symptoms of allergy or any unexpected health event) will be also presented.

7. **Ethics**

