9.10 Food consumption record

Food consumption record

Screening ID

Randomisation ID

You are required to eat 2 pancakes from each packet every day.

Please use this sheet to record each day that you eat the pancakes, and note any days that you do not eat them. Also write down if you only eat part of the portion.

The researcher will highlight your start and end dates on this sheet.

Today's date _____

Researcher signature _____

	Mon	Tue	Wed	Thu	Fri	Sat	Sun
Week 1							

	Mon	Tue	Wed	Thu	Fri	Sat	Sun
Week 2							

	Mon	Tue	Wed	Thu	Fri	Sat	Sun
Week 3							

	Mon	Tue	Wed	Thu	Fri	Sat	Sun
Week 4							

	Mon	Tue	Wed	Thu	Fri	Sat	Sun
Week 5							

Thank you for your help!

9.11 Clinical Research File – Screening – Visit 1

Visit 1 Screening CRF

Contact details	
ID	
First name	
Surname	
Telephone number	
Mobile number	
Email	
Home address	

General information		
Gender	MALE	FEMALE
Date of Birth		<18 or >80 y = exclude (<January 1934 to September 1996>)

Date & Time of examination:

Physical examination	Measurement	Fits MS Criterion? (Y / N)	MS Criterion
Height (m)			
Weight (kg)			
Waist circumference (cm)			Male ≥102 cm Female ≥88 cm
Systolic BP (mm Hg)			≥130 mm Hg
Diastolic BP (mm Hg)			≥85 mm Hg

Date & Time of blood collection:

Blood analysis	Analyte concentration	Fits MS Criterion? (Y / N)	MS Criterion
Triglycerides (mg/dL)			≥150 mg/dL
Total cholesterol (mg/dL)			
HDL-cholesterol (mg/dL)			Male ≤40 mg/dL Female ≤50 mg/dL
Glucose (mg/dL)			≥110 mg/dL

MS criteria met (please tick those which apply)

Waist Circumference	Blood Pressure (SBP &/or DBP)	Triglycerides	HDL-cholesterol	Glucose	Number of MS criteria met

Continue to page 2

GP contact details	
GP name	
Surgery name	
Telephone number	
Surgery address	

End of Visit 1 Screening CRF

Visit 2 Baseline CRF

Randomisation ID

Screening ID

Date & Time of examination:

.....

Physical examination	Measurement	Fits MS Criterion? (Y / N)	MS Criterion
Height (m)			
Weight (kg)			
Waist circumference (cm)			Male ≥102 cm Female ≥88 cm
Systolic BP (mm Hg)			≥130 mm Hg
Diastolic BP (mm Hg)			≥85 mm Hg

Date & Time of blood collection:

.....

Blood analysis	Analyte concentration	Fits MS Criterion? (Y / N)	MS Criterion
Triglycerides (mg/dL)			≥150 mg/dL
Total cholesterol (mg/dL)			
HDL-cholesterol (mg/dL)			Male ≤40 mg/dL Female ≤50 mg/dL
Glucose (mg/dL)			≥110 mg/dL

MS criteria met (please tick those which apply)

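### Randomisation is stratified by sex, but the stated primary model omits sex; if sex predicts the 4-week change, between-BEF standard errors are somewhat too large (minor)

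*Protocol*

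**What the plan says.** **Randomisation (Protocol 6.1).** Allocation uses "predefined randomization lists created separately for each pilot study". Each list "will be prepared with a sample size of 120, with a block size of 5 and with an allocation ratio of 1:1:1:1:1". Sex is an explicit stratum: "Gender will be considered as a stratum with a ratio near to 1:1". The numbers run "from 101 to 160 for male and from 201 to 260 for female participants".

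**Analysis (Protocol 6.4).** The response is the mean change in TG and in HDL-C, and each "will be analyzed with a mixed linear model including food matrix and type of enrichment as fixed effects". Secondary endpoints are to be analysed similarly. Pairwise comparisons follow only if the model shows a significant difference among groups. Sex is not named here or in any other analysis text.

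Each centre tests one food matrix, so the food-matrix term also carries centre. Sex is therefore the one stratification factor that the stated model leaves out.

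**The concern.** Blocking within sex removes the sex component from the true sampling variation of a difference between arms. A model without sex does not know this and counts any sex-related spread in the change scores as residual noise. The reported standard errors are then either right or too large, never too small, and the tests are correct or conservative.

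What is at stake is sensitivity. The arms have 20 participants each, and the pairwise comparisons open only after a significant overall result. A conservative overall test can therefore keep closed the comparisons between BEFs that the pilot is meant to inform.

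Balance may also not survive follow-up. The full analysis set needs primary outcome data at both visits, and withdrawn volunteers are replaced from 20 spare numbers per pilot. The Protocol does not say that a replacement takes the product of the person replaced. A model with sex in it would absorb any imbalance that results.

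**Working it through.** **1. Counts from Sections 3.2 and 6.1.** Arms: 5 × 20 = 100 per centre, and 3 × 100 = 300. Lists: 60 male + 60 female numbers = 120. For each sex, 60/5 = 12 blocks, so 24 numbers per arm in all. With 50 of each sex enrolled, 50/5 = 10 complete blocks, giving 10 men and 10 women in every arm. The design does balance the arms on sex.

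**2. No stated power to reproduce.** Section 3.2 says only that "20 subjects per arm would be sufficient to obtain measurable changes for the parameters that will be tested". It gives no alpha, power, effect size or SD. The following are therefore assumptions: two-sided alpha 0.05, 80% reference power with sex in the model, and a share R² of the change variance due to sex between 0 and 10%.

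**3. Formulas under balance (normal approximation).**
- SE inflation = 1/√(1 − R²) − 1
- Coverage of a nominal 95% between-arm interval = 2Φ(1.96/√(1 − R²)) − 1
- Actual alpha = 1 − coverage
- Power without sex = Φ(2.80 − 1.96/√(1 − R²)), where 2.80 = 1.96 + 0.84
- With the sexes 1:1, the sex difference in change that gives R² is s = 2√(R²/(1 − R²)), in within-sex SDs

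| R² (assumed) | s | SE inflation | Coverage | Actual alpha | Power without sex |
|---|---|---|---|---|---|
| 0 | 0 | 0% | 95.0% | 0.050 | 80% |
| 2% | 0.29 | 1.0% | 95.2% | 0.048 | 79% |
| 5% | 0.46 | 2.6% | 95.6% | 0.044 | 79% |
| 10% | 0.67 | 5.4% | 96.1% | 0.039 | 77% |

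**4. Check by simulation.** One centre was simulated with five arms of 10 men and 10 women and within-sex SD 1 (20,000 runs per setting). The true difference was 0.886 SD, which gives 80% power by the normal formula at 20 per arm.

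| s | True SD of the contrast, either model | Mean reported SE, sex omitted | Mean reported SE, sex included | Power, omitted / included |
|---|---|---|---|---|
| 0 | 0.317 | 0.315 | 0.315 | 79.6% / 79.6% |
| 0.5 | 0.312 | 0.326 | 0.315 | 77.4% / 79.2% |
| 0.8 | 0.315 | 0.341 | 0.315 | 74.0% / 79.1% |
| 1.0 | 0.316 | 0.354 | 0.315 | 71.4% / 78.9% |

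The estimate and its true spread are the same with or without sex; only the reported SE moves. The last two rows correspond to R² of about 14% and 20%, beyond the range used above, and show how the effect grows. A three-centre version gave the same pattern.

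**5. If balance is lost.** Suppose, purely for illustration, that one arm loses two of its ten men and another loses nobody. The proportions of men are 8/18 = 0.444 and 0.500. With s = 0.5, the unadjusted contrast shifts by 0.056 × 0.5 = 0.03 SD. That is small, but a model with sex removes it.

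**The case against.** **The list of terms is not closed, and no SAP is at hand.** The Protocol speaks of a model that includes the two named factors, so a SAP could add sex. This is fair, and it is one reason to keep the grading low. Still, the Protocol does name its model terms, and as written they do not match its own randomisation.

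**A reader might infer that the error bars are too wide as a matter of fact.** The documents do not show this. The endpoint is change, and nothing in them says that men and women change differently over four weeks. With no such difference the loss is zero.

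**The sex-specific entry cut-offs might be taken as proof of a sex effect.** For HDL-C they are "Male ≤40 mg/dL Female ≤50 mg/dL", and for waist 102 and 88 cm. These concern levels, which a change score largely removes, and waist is not a primary endpoint. The TG cut-off is the same for both sexes. Entry can also be through TG alone, so the HDL-C cut-off does not fix where men and women start.

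**A reader might say that the benefit of stratifying is thrown away, or that R² × 300 = 6 to 30 participants' information is discarded at R² of 2 to 10%.** Neither follows. Under balance the estimates, their true variance and the ranking of the BEFs are unchanged; only the reported precision is understated. Nor is any planned power lost, because the Protocol states none.

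**The effect is small and this is an exploratory pilot.** That stands. The only 95% intervals that Section 6.4 explicitly promises are for changes from baseline, so the coverage figures above apply to the between-arm comparisons that would accompany the post-hoc tests.

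**Conclusion.** The mismatch is plain on the page: sex is a randomisation stratum in every pilot, and the stated model does not contain it. The consequence is conditional. If sex predicts the 4-week change in TG or HDL-C, reported standard errors for between-BEF differences are too large and the tests are conservative. Type I error is not inflated, and under balance there is no bias.

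Over the assumed 0 to 10% range, the cost in power against an assumed 80% reference is at most about 3 percentage points, and about 2 points or less up to a sex difference in change of 0.5 SD. The sizes rest on the assumed R², alpha and reference power, on arms balanced by sex, and on a roughly 1:1 sex ratio. Severity is minor. The mismatch itself is certain; the size of its effect in this trial is unknown.

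**What to change.** In Section 6.4, add sex as a fixed effect to the models for TG, HDL-C and every secondary endpoint. Because the lists are made separately for each pilot, a sex-by-food-matrix term may be added as well so that the model matches the strata exactly; this is optional. If sex is deliberately left out, give the reason.

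The cost is one line of text and 1 degree of freedom for sex, or 3 with the interaction (1 + 2). With 300 participants, the residual has 300 − 7 = 293 degrees of freedom for a model with additive matrix and enrichment effects, or 300 − 15 = 285 if all 15 BEF means are fitted. No new data are needed: sex is recorded on the telephone screening questionnaire and the Visit 1 CRF, and the randomisation number ranges identify it. The Visit 2 and Visit 3 CRFs carry no sex field, so the value has to be taken from the screening record.

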Many naturally-occurring compounds in dietary plants and animal products possess a variety of physiological functions which promote human health and wellbeing, and contribute to better diet-related-disease (DRD) prevention and particularly the Metabolic Syndrome (MS). These compounds, known collectively as bioactives (natural components of foods that possess biological activity in addition to their nutritional value), normally occur at very low concentrations in foods, and their effects on human health are being studied intensively for their possible contribution toward reducing the risk of many DRDs. Identifying bioactives, establishing their mechanisms of actions and health effects are all active areas of scientific inquiry and, through industrial exploitation, potential societal benefit.

Scientific understanding of the role and mechanisms of bioactives is fragmented. Research often addresses the theoretical possibility of health improvement effects rather than their real, practical use for everyday diets. Bioactives cannot be considered as discrete chemical compounds and research must focus on bioactive-enriched foods (BEF), if consumer demands for foods delivering appropriate health and wellbeing benefits are to be fulfilled. The general objective of PATHWAY-27, a pan-European interdisciplinary team of 16 life/social scientists and 10 high tech/ food processing SMEs, addresses the exploitation of bioactive compounds as ingredients of foods that, within the common diet, could significantly benefit human health and wellbeing. PATHWAY-27 will evaluate the effectiveness of docosahexaenoic acid (DHA) alone or in combination with two other bioactives, beta-glucan (BG) and anthocyanins (AC), chosen for known/claimed effectiveness in reducing some risk factors of MS. These compounds will be considered as ingredients of BEFs enriching three different widely consumed food matrices (dairy-, bakery-, egg products) and not pure compounds. This will allow us a better understanding of possible synergisms and bioactive matrix interactions.

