BEFs to be tested in PATHWAY-27 clinical studies will be designed and selected in preceding work packages of this European FP7 project. SMEs will be deeply involved in the elaboration of BEFs. The purpose of pilot clinical studies will be to select, for each of the three food matrices, the BEF delivering the greatest reduction in serum triglycerides (TG) or increase in HDL-cholesterol (HDL-C). Three pilot studies will be conducted in three clinical research centres (Max Rubner Institute, Karlsruhe, Germany; University of Leeds, United Kingdom; and Human Nutrition Research Centre of Auvergne, France), each participating centre focusing on a specific food matrix. Each pilot study will be randomized and double blind and aim to identify the most active BEF within a specific food matrix. The BEFs selected after pilot studies will then be tested in the subsequent, larger interventional study, on their ability to modulate a wider range of metabolic outcomes.

2. Aim

The aim of this multi-centre, randomized, double blind, parallel pilot dietary intervention study is to identify the BEF achieving the greatest effect on lipid parameters. Three different matrices, dairy-, bakery-, and egg products, containing DHA, BG and AC given alone or DHA associated with BG or AC will be tested. Thus, 15 products, five in each centre will be tested.

3. Study population

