9.6 SOP Quantification of triglycerides in serum samples

Standard Operating Procedure (SOP) Quantification of triglycerides in serum samples

Purpose and scope

This SOP describes the procedures that all study personnel will use when analyzing serum samples for the quantitative determination of serum triglycerides as part of PATHWAY-27 WP5, while ensuring the safety and welfare of subjects and staff involved in the study.

Responsible persons

Principal investigator

The principal investigator is responsible and accountable for:

1. Ensuring that the equipment is fit for purpose.
2. Ensuring that all staff is suitably trained in all aspects of the procedure, including the safe handling of blood-derived samples and chemicals.
3. Notifying the WP leader of any deviations, safety breaches or abnormal results.
4. Keeping record of the code of all subjects entering the study, guaranteeing their data will be anonymous

Clinical researcher or manager

The clinical researcher or manager is responsible for:

1. Reporting to the principal investigator the results of analysis and logs of all procedures undertaken, highlighting any deviations, safety breaches or abnormal results
2. Operator
3. The operator is responsible for:
4. Following all procedures according to the SOP and instructions provided, including the keeping of logs of calibration and control procedures.
5. Notifying the clinical researcher/manager or principal investigator of any deviations or abnormal results.

Procedures

Name of the method

Automated enzymatic colorimetric method for determination of triglycerides.

Purpose

For the in vitro diagnostic use in the quantitative determination of triglycerides from serum using an automated blood analyser.

Principle

The method relies on the enzymatic hydrolysis of triglycerides to fatty acids and glycerol. Glycerol is then oxidized to dihydroxyacetone and hydrogen peroxide. Hydrogen peroxide can be measured following a Trinder endpoint reaction, the products of which can be detected by colorimetry at wavelengths >505 nm. The single reagent procedure measures total triglycerides including the mono and diglycerides and the free glycerol fractions.

Equipment

Automated blood analyser. Manufacturer varies between countries therefore cannot be harmonized. However, the analyses will focus on variations of this parameter from d0 to d28 that would not be affected by the lack of analyser harmonisation.

Reagents

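### The pooled primary model, as named in section 6.4, estimates the best enrichment on average over the three matrices, while the stated aim is to select the best product within each matrix

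*Protocol*

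**What the plan says.** **Purpose.** Section 1 (Background – Introduction) says the pilots are to "select, for each of the three food matrices, the BEF delivering the greatest reduction in serum triglycerides (TG) or increase in HDL-cholesterol (HDL-C"). Each pilot is to "aim to identify the most active BEF within a specific food matrix".

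**Design.** There are three centres and three matrices, with "each participating centre focusing on a specific food matrix". Section 6.3.1 repeats this: "The complete sample size will be equally distributed between three centres responsible for either bakery, dairy or egg products". Section 6.1 provides a separate randomisation list for each pilot, with equal allocation to five enrichments. Section 3.2 gives 20 participants per arm.

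**Analysis.** Section 6.4 has the mean changes in the two primary endpoints "analyzed with a mixed linear model including food matrix and type of enrichment as fixed effects". It continues: "If the model indicates significant differences among groups, post-hoc tests will be applied for pair wise comparisons". It names neither a matrix-by-enrichment term nor an analysis by matrix. It also promises descriptive mean changes with 95% confidence intervals, without saying whether these are given per product or whether they decide the selection.

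**Laboratory.** On the analysers, the triglyceride procedure (section 9.6) says: "Manufacturer varies between countries therefore cannot be harmonized". It relies on change from baseline to remove the difference.

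**The concern.** The decision is made three times, once per matrix, each time among five products compared by randomisation within one centre. The named model pools the three pilots and gives each enrichment a single effect common to all matrices. That answers a different question from the one in section 1. It is the right simplification only if the effect of an enrichment does not depend on the food carrying it. The protocol nowhere makes that assumption, and its introduction to the wider programme leaves the matter open: "This will allow us a better understanding of possible synergisms and bioactive matrix interactions".

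The selected products go forward to the larger interventional study, so a wrong choice in one matrix would be carried into that trial.

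A secondary matter is how differences between matrices will be read. Nobody is randomised to a matrix, and matrix coincides with centre, country and analyser. Section 6.4 does not confine its post-hoc comparisons to products of the same matrix.

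**Working it through.** **1. The plan's own figures.** 3 matrices × 5 enrichments × 20 = 300 participants, and 5 × 20 = 100 per centre; both agree with the protocol. No alpha, power, effect size or SD is stated, so no power figure can be reproduced. The effect sizes below are assumptions, in units of the SD of change.

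**2. What the named model estimates.** With only the two named effects, the expected change for enrichment *j* in matrix *i* is μ + αᵢ + βⱼ. For two enrichments *j* and *k* in the same matrix, the difference is

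(μ + αᵢ + βⱼ) − (μ + αᵢ + βₖ) = βⱼ − βₖ,

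which does not involve *i*. The fitted order of the five enrichments is therefore the same in every matrix. With equal arms, βⱼ − βₖ is estimated by the difference of means over 60 participants each, averaged across the three matrices. Fitting this model to a simulated 300-row data set in which the best enrichment differed by matrix gave the same order of enrichments in all three.

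**3. Parameters.** The additive model has 1 + 2 + 4 = 7 parameters. Adding the interaction brings in 2 × 4 = 8 more, making 15: one mean per product.

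**4. Consequence for selection.** Arm means were simulated with standard error 1/√20. In each matrix one arm was truly best by the stated advantage and the other four were equal. The entries are the percentage of matrices in which the truly best product was chosen, pooled ranking against within-matrix ranking.

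| Truth | 0.3 SD | 0.5 SD | 0.8 SD |
|---|---|---|---|
| Different winner in all three matrices | 28 v 60 | 31 v 84 | 33 v 98 |
| Same winner in two matrices, another in the third | 46 v 60 | 58 v 84 | 64 v 98 |
| Same winner in all three | 86 v 60 | 99 v 84 | 100 v 98 |

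In the first two rows the pooled ranking is never right in all three matrices, because a single common winner cannot be. At 0.5 SD, within-matrix ranking is right in all three in 59% of trials.

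**5. Precision.** The standard error of a pairwise enrichment difference is √(2/60) = 0.183 SD pooled and √(2/20) = 0.316 SD within one matrix.

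**6. Matrix and centre.** Each centre has exactly one matrix, so the centre and matrix indicators are identical columns. Adding centre to the additive model takes it from 7 to 9 columns while the rank stays at 7. No analysis can separate the two, and the interaction term does not help, since matrix-by-enrichment is also centre-by-enrichment. Taking changes from baseline removes a constant offset between analysers but not a proportional calibration difference.

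**The case against.** **An interaction is not ruled out.** Section 6.4 says the model includes the two effects; it does not say they are the only ones, and a statistical analysis plan could add a term. This stands as a limit: a reader might infer that the protocol forbids an interaction, and it does not. But the protocol chose which effects to name, and on the natural reading those do not serve its own aim. That is a mismatch between stated analysis and stated aim, and more than an omitted detail.

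**The groups may be the product arms.** Section 6.3.1 uses the word for the five arms in a centre, so the post-hoc tests could be meant at product level. That is possible, but a strictly additive model gives no separate product contrasts to test. If all 15 products were compared, there would be 15 × 14 / 2 = 105 pairs, of which 3 × 10 = 30 lie within a matrix and 75 cross matrices without randomisation. The text does not settle which is meant.

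**Selection need not use the model.** A reader might infer that the trial cannot select a product per matrix, or will select the wrong one. The documents do not support that: descriptive mean changes could rank the five arms within a matrix if reported by product. What stands is that no rule ties the selection to them.

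**The simulation depends on its scenario.** This is true. The 31% comes from assuming a different winner in every matrix. When the winners agree, pooling is better. Only one endpoint was simulated, although selection rests on TG or HDL-cholesterol.

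**Confounding with centre is not an error.** Agreed. A reader might take it as biasing the choice of product. One matrix per centre is stated openly, comparisons within a matrix are randomised within one centre, and a proportional calibration difference would not reorder arms there. No passage says that matrix differences will be interpreted as product effects.

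**The sentence on interactions describes the whole programme.** This is also fair. It shows that the programme leaves interaction open, but testing for it is not given as the pilots' purpose.

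**Conclusion.** The point holds as a mismatch between the named primary model and the per-matrix aim. On the natural reading of section 6.4, the model estimates which enrichment is best on average over three centres, and its ranking cannot differ by matrix. The algebra needs no assumption beyond that reading.

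The practical size does depend on assumptions. If the best enrichment varies by matrix, a ranking from this model is wrong in at least one matrix. At an assumed 0.5 SD advantage, the share of correct choices runs from 31% against 84% (all winners differ) to 99% against 84% (all agree, where pooling gains). These figures illustrate what rests on the no-interaction assumption; they are not a forecast of the trial's error rate.

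The coincidence of matrix with centre is secondary. It limits what may be said between matrices and leaves the randomised comparisons within each matrix unbiased.

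**What to change.** In section 6.4:

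- Analyse each pilot (matrix) separately, or add matrix-by-enrichment to the pooled model. The two are not fully equivalent: the estimated product means are the same, but the pooled model shares one residual variance across centres.
- Base the post-hoc comparisons and the selection of the product on enrichment contrasts within each matrix, and say so.
- State that differences between matrices are not randomised and cannot be separated from centre and analyser, so they will not be tested post hoc or interpreted as matrix effects.

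This changes wording only; sample size, randomisation and data collection stay as they are. The price is precision: 20 rather than 60 participants behind each enrichment mean, so the standard error of a pairwise difference rises from 0.183 to 0.316 SD. Twenty per arm is the size that section 3.2 already regards as sufficient within each matrix.
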